## **Synopsis**

### **Purpose**

### PRIMARY PROBLEM ADDRESSED

Current evidence-based type 1 diabetes mellitus (T1D) self-management interventions target glycemic control but ignore other modifiable health concerns prevalent in T1D such as hypertension and obesity. Exercise interventions could provide a novel solution if they could innovatively address the diabetes management and psychosocial challenges around exercise posed by T1D. These include especially keeping blood glucose in a safe range during and after exercise (i.e., glycemic stability), and overcoming the fear of hypoglycemia.

### **PRIMARY PURPOSE**

Develop a data-driven exercise intervention for T1D and evaluate its feasibility, acceptability, and mathematical robustness.

### **SECONDARY PURPOSE**

Determine mechanisms underlying the link between T1D-related barriers (glycemic stability, fear of hypoglycemia) and physical activity behavior.

### **Objectives**

### **PRIMARY OBJECTIVES**

- **1-1.** Evaluate the intervention for feasibility.
- **1-2.** Evaluate the intervention for acceptability (i.e., user satisfaction).
- **1-3.** Evaluate the intervention app algorithm's accuracy to predict lapses in exercise behavior ahead of time.

### **SECONDARY OBJECTIVES**

- **2-1.** Examine whether recognized T1D-related physical activity barriers (fear of hypoglycemia, glycemic variation) predict momentary and long-term variation in motivation states for physical activity.
- **2-2.** Examine whether motivation states for physical activity predict momentary and long-term variation in physical activity behavior change, adherence, and maintenance resulting from a T1D motivational physical activity intervention.
- **2-3.** Qualitatively identify determinants and sequalae of motivation states for physical activity among adults with T1D.

### **Study Population**

Adults 30-65 years old with T1D and sedentary lifestyle at baseline, because people with T1D experience unique barriers to exercise that must be addressed by intervention. The age range was chosen because those below it have significantly different needs regarding exercise (exercise dependence, desire to improve body image) and self-management (transitions in care, residence, and professional life), while those above it have significantly different needs regarding exercise including mobility issues and substantial modifications to exercise.

### **Number of Participants**

This is a pilot study with primary objectives to test feasibility and acceptability, for which a typical sample size is 10-40 participants. Within this range we chose 24 participants to first ensure thematic saturation of interviews and second achieve adequate power for one of the secondary objectives. Further detail in section 7.1.

### **Study Design**

Single group completing familiarization (2 weeks), intervention (4 weeks) and follow-up (2 weeks) with longitudinal quantitative observations (surveys, wearable biosensors) and a descriptive qualitative interview.

### **Study Duration**

16 months (data collection) plus 4 months (data analysis). Each subject participates for 9 weeks counting the time to consent and mail supplies.

### **Outcome Variables**

Primary Objective #1 (Feasibility):

\*Participant use metrics (i.e., % completion of diary, % wear-time of biosensors, frequency of video usage, % received of text messages)

### Primary Objective #2 (Acceptability):

\*Likert-style survey of satisfaction with specific components of this intervention

\*Interview themes

### Primary Objective #3 (Mathematical robustness):

\*Biosensor readings of blood glucose and exercise

### Secondary Objective #1 (prediction of motivation states):

\*Predictors: Biosensor readings (blood glucose, physical activity, sleep), surveys (fear of hypoglycemia)

\*Dependent variable: Motivation states for physical activity

### Secondary Objective #2 (prediction of physical activity):

\*Predictor variable: Motivation states for physical activity

\*Dependent variable: physical activity behavior

Protocol Number 2000035846

### August 13, 2024 Version #7

### Secondary Objective #3 (qualitative):

\*Interview themes

### Online locations:

- \*OneDrive for data storage
- \*REDCap for weekly study visit survey capture
- \*Ilumivu for mobile survey capture
- \*Qualtrics for mobile survey capture
- \*GlucoseZone mobile app for intervention delivery and capture of wearable device data from Dexcom and Fitbit
- \*InPen user dashboard for insulin injection data capture
- \*Keto-Mojo researcher dashboard for capture of ketone data

# **Abbreviations**

Abbreviation	Explanation
API	Application programing interface
BG	Blood Glucose
ССВМ	Continuous glucose monitor
CRAVE	Cravings for Rest and Volitional Energy Expenditure (CRAVE) survey of motivation states for physical activity
EP	Exercise physiologist
JDAT	Joint Data and Analytics Team
RA	Research Assistant
SCT	Social Cognitive Theory
T1D	Type 1 Diabetes
WANT	Wants and Aversions for Neuromuscular Tasks
YSM	Yale School of Medicine

# **Glossary of Terms**

Glossary	Explanation
Cravings for Rest and Volitional Energy Expenditure (CRAVE) survey of motivation states for physical activity	Survey asking about momentary motivation to move or be still. Construct relates to motive states, affective valence (pleasure/displeasure), and arousal/activation.
Ecological momentary assessment	Repeated sampling of behaviors and experiences in real-time, which serves to a) minimize recall bias and b) capture the effect of real-world surroundings.
Just-in-time adaptive messaging	"An intervention that adapts the provision of support (e.g., the type, timing, intensity) "over time to an individual's changing status and contexts with the goal to deliver support "at the moment and in the context that the person needs it most and is most likely to be receptive." 

# **Protocol Revision History**

Version Date	Summary of Substantial Changes
7/20/23	First submission
7/24/23	Added HIC protocol number
11/6/23	More precise safety guidance, formal template for goal-setting, increased compensation, recruitment wording and methods, audio recording frequency and method, additional research site, survey question corrections,
12/5/23	Raised blood pressure exclusion criteria
1/16/24	Added requirement for PCP confirmation of eligibility, further clarified exclusion criteria with specific conditions, replaced exercise coach with exercise physiologist, added surveillance protocol for monitoring symptoms, added data and safety monitoring board (DSMB)

August 13, 2024 Version #7

# 1 Background

### 1.1 Background

**PRIMARY AIMS: EXERCISE SUPPORT** 

Exercise for type 1 diabetes (T1D) is an important area for intervention development.

Intensive diet and insulin self-management are required for people with T1D to mitigate snacking, physical activity, and mental stress-associated glycemic fluctuations. There are several modifiable cardiovascular risk factors including overweight (60%), hypertension (40%), dyslipidemia (60%), and inadequate physical activity (67%-82%) exacerbating their already elevated risk of cardiovascular morbidity and mortality. Existing T1D self-management interventions (psychoeducation, diabetes devices, digital platforms) have improved achievement of glycemic targets, however none of the current interventions are effective for cardiovascular risk factors or lifestyle behaviors when measured with reliable instruments. For instance, intensive insulin therapy in the Diabetes Control and Complications trial while decreasing HbA1c increased risk of developing obesity, and this weight gain correlated with lipid panel and blood pressure deteriorations. Thus, T1D self-management interventions that address health targets beyond glycemic control are needed. Physical activity interventions can improve health outcomes (e.g., aerobic capacity, lipid profile). Unfortunately, most people with T1D do not regularly engage in physical activity indicating a need for novel interventions.

For purposes of describing this study, T1D will also refer to other types of diabetes that present similarly from the standpoint of behavioral self-management considerations. These types are the others with absolute insulin deficiency: latent autoimmune diabetes of adulthood and diabetes secondary to pancreatitis.

# Physical activity with T1D has been linked to glycemic destabilization and fear of hypoglycemia.

Lack of engagement in physical activity stems from the unique challenges of physical activity with T1D. Physical activity with T1D can dysregulate blood glucose, leading to hypo- and/or hyperglycemia during and up to 24hr later due to consumption of energy, increased insulin sensitivity, release of counterregulatory hormones, and various combinations thereof. The direction and magnitude of these glycemic fluctuations vary according to type of physical activity, personal insulin sensitivity, insulin-on-board, and hormone concentrations. There is also high interindividual variation in these responses due to factors not well understood. Predicting these fluctuations to adjust diet and insulin is challenging.

When these fluctuations bring blood glucose into clinically unsafe ranges, symptoms can require halting of physical activity. As well, a context where these symptoms are likely (e.g., downward-trending blood glucose or high insulin-on-board) can preclude the start of physical activity. Furthermore, repeated exposure to these symptoms leads to *fear of hypoglycemia*, the most reported barrier to physical activity among people with T1D. This fear can motivate people with T1D to avoid physical activity due to remembering past symptoms and anticipating future occurrence of symptoms.

This investigation does not address exercise for type 2 diabetes (T2D) which faces different barriers compared to T1D. There is less risk of hypoglycemia due to the nature of the medication treatment, and therefore less fear of hypoglycemia. Meanwhile there is greater associated stigma, since the disease has etiology rooted in modifiable lifestyle behaviors. In addition, obesity as a comorbidity is more common and more severe. Therefore there is greater relevance of obesity-related barriers such as joint pain, exercise equipment being too small, and weight stigma.

August 13, 2024 Version #7

[figure not shown]
### Knowledge and technology are available that could support exercise for T1D.

Patients and their providers are encouraged to follow consensus statement guidelines for monitoring blood glucose levels and adjusting diet and insulin before, during, and after exercise to limit safety hazards and optimize benefits26. In addition, continuous glucose monitoring (CGM) is a now widely used (30%) technology among people with T1D that can support them to follow these exercise recommendations. First, by giving glucose trends rather than "snapshot" values. CGM helps the patient identify risk of exercise-induced hypo- or hyperglycemia and adjust insulin and diet accordingly and mitigate fear of hypoglycemia. Second, CGM presents users with time-series feedback of their glucose levels, allowing them to infer whether the timing of behaviors such as exercise (e.g., morning vs. afternoon, after vs. before insulin bolus) contributes to achievement of the target range. Patients with *type 2* diabetes have shown greater motivation to increase exercise when presented with feedback on the intersection of exercise and CGM data. Third, patients using CGM report better confidence in glycemic control and motivation to more carefully consider lifestyle choices. combination of knowledge and technology holds great potential to help people with T1D overcome barriers to exercise. Yet, evidence-based interventions to translate CGM feedback into sustainable adherence to exercise-related behaviors are lacking.

### Translating this Knowledge and Technology to Practice

Most CGM users regularly view the real-time display of current blood glucose values and trending direction but few use mobile medical applications to comprehensively view CGM data (17%). These metrics are discussed with providers at clinic appointments, but provider discussions often do not translate to daily self-management decisions by patients. *Studies working with people with T1D to develop and test how they could independently use in-depth CGM information to promote safe, consistent, and effective exercise represent an underexplored, promising area for intervention development.* 

We propose to address the gap between the available relevant medical information and translation to successful exercise by people with T1D by applying the Information-Motivation-Behavioral Skills (IMBS) model (Figure 1). The IMBS model has been successfully applied to self-management interventions for T1D and other chronic diseases and explained variance in self-management outcomes. In the present application, we propose to develop mobile tools that leverage the diabetes literature, CGM data, and informatics to derive the needed components of IMBS for exercise (information about exercise, motivational encouragement to exercise, and feedback on long-term exercise outcomes) and deliver it to people with T1D.

**Figure 1.** Information-motivation-behavioral skills (IMBS) model for exercise with type 1 diabetes.

### SECONDARY AIMS: PSYCHOLOGICAL MECHANISMS FOR BEHAVIOR CHANGE

August 13, 2024

Version #7

[figure not shown]
# Rationale for determining real-time mechanisms underlying physical activity behavior and T1D-related barriers.

Fear of hypoglycemia has been measured as a "trait" (i.e., personality-specific) but in just one study as a "state" (i.e., situation-specific). Participants reported their state fear of having hypoglycemia over the next 12hr. Responses had significant intraindividual variation and correlation with the related construct of blood glucose variability, indicating the need to further study fear of hypoglycemia as a state variable. Glycemic destabilization meanwhile is recognized to cause intense symptoms that acutely preclude physical activity, but no study has addressed the possible impact of more nuanced changes. E.g., downward-trending glucose could affect motivation to be active even if not projecting an excursion outside the clinically safe range.

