# STUDY PROTOCOL

# **Social Behavioral Template**

#### 6.1.1 Data Collection

#### STUDY DESIGN OVERVIEW

The study is a single-group longitudinal study with periods of familiarization with devices, intervention using devices and mobile app, and maintenance follow-up (Figure 4). The primary aim is observing the intervention for feasibility, acceptability, and mathematical robustness. The secondary aim is observing psychological and biometric outcomes through assessments (Table 2) which are completed 1x/weekly during the entire study to test long-term effects (hypothesis 2-1-2 & 2-2-1) and 5x/daily during maintenance follow-up to test momentary effects (hypothesis 2-1-1 & 2-2-2). The secondary aim also includes an interview at the end of the study (hypothesis 2-3).

**Figure 4.** Individual participant timeline. Blue indicates measures for primary aims and red indicates measures for secondary aims.

Table 2. Surveys used for secondary aims. Appendix has instruments for dependent variable (#2a,2b), independent

variables fear of hypoglycemia (#3a, 3b), exercise self	-efficacy (#4), exercise self-regulation (#	
valence (#6), daily intention and competing demands  PHASE	Momentary	Weekly
	(Hypotheses 2-1-1, 2-2-2) (Timepoints T1-T2)	(Hypotheses 2-1-2, 2-2-1) (Timepoints T0-T2)
ASSESSMENT SCHEDULE	5x daily at random times within 3hr bins under ambulatory conditions of daily living	Weekly in controlled setting (tele-video in quiet room)
DEPENDENT VARIABLE††		
Cravings for Rest and Volitional Energy Expenditure (CRAVE) survey of motivation states for physical activity*	Score of 1-item want "right now" and 1-item aversion "right now"	Score of 5-item want "past week" and 5-item aversion "past week"
INDEPENDENT VARIABLES		
Fear of hypoglycemia†	Score of 1-item "next 3 hours" version	Weekly score of 18-item "past week" version
Fear of hyperglycemia ††	Score of 1-item "next 3 hours" version	Weekly score of 24-item "past week" version
Blood glucose metrics‡	Past 3 hours averages and slope	Weekly averages
Exercise self-efficacy 	N/A	Weekly score of 9-item "past week" version
Exercise self-regulation 	N/A	Weekly score 15-item "past week" version
COVARIATES		
Non-T1D-related affective valence states previously associated with CRAVE score (pleasure/displeasure  , activation/arousal  ).§	Score of 1-item "right now" versions	Weekly score of 1-item "past week" versions
Day of week, time of day	Timestamp	N/A

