# 7 Statistical Design

#### 7.1 Sample Size Considerations

This is a pilot study with primary objectives to test feasibility and acceptability, for which a typical sample size is 10-40 participants¹. Within this range we chose 24 participants to first ensure thematic saturation of interviews (aims 1-2, 2-3), and second achieve adequate power for one of the secondary objectives, specifically hypothesis 2-1-1. Based on my past retention and adherence among sedentary adults with and without T1D (88% participants completed, they provided 83% of ecological momentary assessments on longer surveys than the present study, 90% continuous glucose monitor wear, and 95% accelerometer wear) I expect 21 completers with an average of 50 complete observations each over T1-T2. Thus, using previous psychometrics of the CRAVE wants and aversions (.28/.39 ICC, 9.9/12.3 total variances) I expect design effects of 14.21/20.11 and standard errors of 0.37/0.48, yielding 91%/81% power to detect predictors having ≥ .34 correlation (e.g., pleasure, fear of hypoglycemia). For other secondary objective hypotheses (2-1-2, 2-2-1, 2-2-2) the study is not designed to detect statistical significance but calculate effect sizes (Cohen's f²) for purposes of determining whether the WANT, SCT model, or both generate a signal for prediction of physical activity behavior.

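### Fear of hypoglycemia is offered as a .34 correlate on a source described as relating it to glucose variability, so the 91%/81% power is not shown to apply to the predictors that Hypothesis 2-1-1 names

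*Combined protocol and SAP*

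**What the plan says.** Section 7.1 chooses 24 participants first for thematic saturation and second to "achieve adequate power for one of the secondary objectives, specifically hypothesis 2-1-1". The Synopsis (Number of Participants) repeats this second reason without naming the hypothesis. The power statement reads "yielding 91%/81% power to detect predictors having ≥ .34 correlation (e.g., pleasure 52 , fear of hypoglycemia 42"; the trailing numbers are reference citations. Section 8.7 III-A carries the same text.

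Section 3.2 states Hypothesis 2-1-1: fear of hypoglycemia and blood glucose trends over the preceding 3 hours predict momentary motivation states. Section 4.2.2 makes the outcomes momentary want and aversion on the CRAVE survey.

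Section 1.1, in the rationale for real-time mechanisms, calls reference 42 the only study to have measured fear of hypoglycemia as a state, with an item covering the next 12 hours, and reports: "Responses had significant intraindividual variation and correlation with the related construct of blood glucose variability". Section 2.1 repeats this. Table 2 in section 6.1.1 lists pleasure/displeasure among the covariates, under "Non-T1D-related affective valence states previously associated with CRAVE score".

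**The concern.** The power statement depends on the size of the correlation between a predictor and want or aversion. For fear of hypoglycemia, the cited source is described in the same protocol as having correlated fear with something else. For glucose trends no figure is offered, and section 1.1 says that the effect of subtler glucose changes has not been studied. Pleasure may have a link to CRAVE through reference 52, but it is not one of the predictors under test.

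Hypothesis 2-1-1 is the only hypothesis for which section 7.1 claims adequate power; the other quantitative secondary hypotheses are set aside for effect-size estimation. Section 1.1 also says that future tailoring would depend on whether glucose or fear turns out to be the predictor. If the figure stands as written, a null result for either may be read as coming from a test with 81% to 91% power.

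**Working it through.** **Source of the .34.** Setting the sections side by side:
- Section 7.1: fear of hypoglycemia, reference 42, is an example of a correlation of at least .34. From context, the correlation is with CRAVE want or aversion.
- Sections 1.1 and 2.1: reference 42 correlated state fear with blood glucose variability, using a 12-hour item. This trial uses a single 3-hour item (Table 2).
- Section 12: reference 42 is dated 2017; the CRAVE development and validation paper (reference 83) is dated 2021.
- No section reports a coefficient for fear or glucose trend against want or aversion.

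**Reproducing the stated power.** Inputs from section 7.1: "I expect 21 completers with an average of 50 complete observations each over T1-T2", so 21 × 50 = 1,050 observations; ICCs .28/.39; total variances 9.9/12.3; and "I expect design effects of 14.21/20.11 and standard errors of 0.37/0.48". Alpha and sidedness are not stated for this hypothesis, so .05 is assumed and both sides are tried.

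Effective N = 1,050 / design effect:
- want: 1,050 / 14.21 = 73.9
- aversion: 1,050 / 20.11 = 52.2

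Standard error = √(variance × design effect / 1,050):
- want: √(9.9 × 14.21 / 1,050) = 0.366
- aversion: √(12.3 × 20.11 / 1,050) = 0.485

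These agree with the stated 0.37/0.48 to within rounding, so the plan did use 21 completers.

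Power by Fisher z = Φ(atanh(r) × √(effective N − 3) − critical z). At r = .34, atanh(r) = 0.354:
- want: 0.354 × √70.9 = 2.98. One-sided, Φ(2.98 − 1.645) = 90.9%; two-sided, Φ(2.98 − 1.96) = 84.6%.
- aversion: 0.354 × √49.2 = 2.48. One-sided, Φ(2.48 − 1.645) = 79.9%; two-sided, Φ(2.48 − 1.96) = 70.0%.

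The bias-corrected version with a t-based critical value gives 91.3%/80.6% one-sided, which is the plan's 91%/81%, and 85.1%/70.7% two-sided.

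**Below .34.** Same Fisher z formula, 21 completers, stated design effects, want/aversion:

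| True correlation | One-sided .05 | Two-sided .05 |
|---|---|---|
| .34 | 90.9% / 79.9% | 84.6% / 70.0% |
| .30 | 83.2% / 70.1% | 74.1% / 58.4% |
| .25 | 69.3% / 55.8% | 57.6% / 43.3% |
| .20 | 52.5% / 41.2% | 40.0% / 29.5% |

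Smallest correlation with 80% power = tanh((critical z + 0.842) / √(effective N − 3)):
- one-sided: tanh(2.486 / 8.42) = .29 for want; tanh(2.486 / 7.02) = .34 for aversion
- two-sided: tanh(2.802 / 8.42) = .32 for want; tanh(2.802 / 7.02) = .38 for aversion

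**Side note.** The want design effect from the stated inputs is 1 + 49 × .28 = 14.72, not 14.21. Using 14.72, want power at .34 is 90.0% one-sided or 83.3% two-sided, so this point is unaffected.

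**The case against.** The power statement is conditional. It gives the power for predictors that reach .34 and does not assert that fear or glucose will. A reader might infer that 91%/81% has no basis at all; the documents do not support that, because the figures follow from the stated inputs at .34 with a one-sided .05 test. This part of the objection stands.

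The same parenthesis cites pleasure from reference 52, which is also the source of the ICCs and variances. Table 2 says such affective states have been associated with the CRAVE score, and section 7.2.1 enters covariates in the same model as the independent variables. Borrowing a related momentary state as a benchmark is a defensible choice in a pilot. That stands too, but the plan does not present pleasure as a stand-in: it lists fear separately, with its own citation.

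A reader might also infer that no estimate for fear exists anywhere. The documents show only that none is given here. The title of reference 42 also mentions self-management behavior, and its coefficients are not visible. The dates argue against a CRAVE correlation in it, but do not show what .34 refers to.

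Finally, the stakes are limited. This is a secondary hypothesis in a single-group pilot, the sample size rests first on the pilot range and thematic saturation, and no decision rule depends on the result.

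**Conclusion.** The concern holds in a limited form. The documents do not show that a correlation of .34 with want or aversion applies to fear of hypoglycemia or to glucose trends, so the stated power is not shown to apply to the predictors under test. The figure itself is valid at .34. With 21 completers and the stated design effects it requires a one-sided .05 test, which the plan does not declare; two-sided it is about 85%/70%.

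The size depends on the true correlation, which the documents leave unknown. At .20, an illustrative value, power is near or below one half on either test. Aversion has no margin even one-sided, since 80% power already needs .34; two-sided it needs .38. These figures assume alpha .05, the Fisher z approximation, and the plan's own design effects and number of completers.

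**What to change.** In sections 7.1 and 8.7 III-A:
- Delete fear of hypoglycemia (reference 42) as an example of a .34 correlation, and say that no estimate is given here for fear or glucose trend.
- State alpha and sidedness for Hypothesis 2-1-1 and quote the figures that match. Two-sided .05: correlations of about .32 (want) and .38 (aversion) are detectable with 80% power, and power at .20 is about 40.0%/29.5%. One-sided .05: about .29 and .34, with power at .20 about 52.5%/41.2%.
- Replace the claim of adequate power with these conditional figures, and make the same change in the Synopsis under Number of Participants.

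In section 7.2.1, report the 2-1-1 effects with 95% intervals, so that a null is read against the detectable correlations.

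The cost is a few sentences and a less favourable stated power. Enrolment does not change.
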